6.5.1 Primary Efficacy Analysis

The proportion of subjects achieving a score of 0 or 1 (none or mild) in LCL severity at maximum smile on the IGA-LCWS at Week 4 after LCL treatment will be summarized. An exact 95% confidence interval for the individual proportions will be provided. A Cochran-Mantel-Haenszel test of association, stratified by baseline IGA-LCWS severity and study center, will be performed. In addition, an exact Cochran-Armitage test for trend, ignoring the stratification factors, will be performed. If the Cochran-Mantel-Haenszel test is significant at the 0.05 significance level, then a linear regression on response will be performed with categorical dose and site as predictors. An unstratified logistic regression analysis may still be used to explore the dose-response relationship.

Additionally, the change from baseline in LCL Severity at Week 4 on the IGA-LCWS at maximum smile will be analyzed using a general linear model with change from baseline as the dependent variable. The model will include baseline severity and study center as fixed categorical effects. The least-square means and standard errors will be presented. Additionally, the differences between dose groups will be presented with corresponding 95% confidence intervals.

[REDACTED]

[REDACTED]

[REDACTED]

[REDACTED]

Statistical Analysis Plan for 1820205

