9.4.1. Efficacy Analyses

Unless otherwise noted, baseline for all efficacy assessments refers to the last available assessment prior to LCL treatment. Efficacy outcomes will be summarized. Descriptive statistics will be provided for all efficacy variables at all timepoints.

The primary efficacy endpoint will be the proportion of subjects achieving a score of 0 or 1 (none or mild) in LCL severity assessed by IGA-LCWS at maximum smile. The LCLs will be evaluated on both sides of the face and both scores will be recorded. If different ratings are obtained from the left and the right sides of the face, subjects will be scored using the higher (i.e., more severe) rating. The dose response in the proportion of responders at Week 4 will be explored using the logistic regression stratified by baseline LCWS severity and study center. Additional measures to assess the effectiveness outcomes will include the investigator GAIS evaluated at maximum smile at each visit. Various responder endpoints associated with the LCWS, such as achieving certain status or certain magnitude of improvement from baseline, will be derived from these effectiveness outcomes for each visit. These responder endpoints will be analyzed by statistical models similar to that for the primary endpoint.

Duration of response will be evaluated by various time-to-event endpoints. Kaplan-Meier (KM) curves will be plotted by dose group for each time-to-event endpoint.

Responder and time-event endpoints defined based on subject assessments for LCL wrinkle severity (such as PLCWS and the subject GAIS for LCL) will be summarized in the same way as those by investigator assessments. Similarly, the endpoints defined based on scores assessed at rest will be summarized in the same way as those on scores assessed at maximum smile.

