6.5.4 Adjustments for Covariates

The analysis of the primary endpoint requires a regression model to be run, where the baseline IGA-LCWS severity and study site are included in the model as covariates.

[REDACTED]

[REDACTED]

[REDACTED]

[REDACTED]

[REDACTED]

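### For the binary primary endpoint, the only regression SAP 6.5.1 mandates is linear, omits baseline severity and runs only after a significant CMH test, in conflict with Protocol 9.4.1 and SAP 6.5.4

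*SAP*

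**What the plan says.** SAP 6.5.1 orders the analysis of the Week 4 response rate as follows.

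- Each cohort's proportion, with an exact 95% interval.
- A stratified test: "A Cochran-Mantel-Haenszel test of association, stratified by baseline IGA-LCWS severity and study center, will be performed".
- A trend test: "an exact Cochran-Armitage test for trend, ignoring the stratification factors, will be performed".
- A conditional regression, should the CMH result be "significant at the 0.05 significance level, then a linear regression on response will be performed with categorical dose and site as predictors".
- A discretionary model: "An unstratified logistic regression analysis may still be used to explore the dose-response relationship".
- A general linear model for change from baseline in IGA-LCWS at Week 4, with baseline severity and center as fixed effects and dose-group differences with 95% intervals.

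Two other places describe the regression differently. Protocol 9.4.1 says the dose response in Week 4 responders "will be explored using the logistic regression stratified by baseline LCWS severity and study center"; the protocol synopsis also names logistic regression. SAP 6.5.4 says the primary endpoint analysis needs a regression "where the baseline IGA-LCWS severity and study site are included in the model as covariates".

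**The concern.** Protocol 9.1 names effective doses and dose response among the uses of these data. A programmer working from the three texts cannot tell which regression to fit to the primary endpoint, whether severity belongs in it, or whether to fit it at all when the CMH test is not significant. The study is open-label, so an unresolved choice could be settled after results are known.

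Two features of the model in SAP 6.5.1 have statistical consequences. An estimate reported only after a significant test is selected for being large. And in a non-randomized study with sequentially enrolled cohorts, leaving out severity exposes the dose comparison to confounding: to reach 0 or 1, a severe subject (3) must improve by at least two grades and a moderate subject (2) by at least one.

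**Working it through.** **1. The texts side by side (binary endpoint only)**

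| | Protocol 9.4.1 | SAP 6.5.1, mandated | SAP 6.5.1, optional | SAP 6.5.4 |
|---|---|---|---|---|
| Model | logistic | linear | logistic | not named |
| Severity | yes | no | no | yes |
| Center | yes | yes | no | yes |
| Condition | none | CMH p<0.05 | discretionary | none; required |

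SAP 6.5.1 departs from Protocol 9.4.1 on model type, severity and conditioning. It departs from SAP 6.5.4 on severity and conditioning, but not on linear form, because 6.5.4 names no model type.

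**2. What remains if the CMH test is not significant**

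Cohort rates and two tests remain. SAP 6.5 adds that differences between cohorts are shown only where the table shells say so. The change-from-baseline model is adjusted and unconditional, but it has a different outcome. So the legible text mandates no dose contrast on the binary endpoint in that case.

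**3. How often the condition is met**

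The plan gives no power figure to reproduce, and no response rates are legible, so all rates below are assumptions. Inputs from the documents: 4 cohorts of about 16 (4 × 16 = 64), 4 sites, 2 severity levels, test level 0.05. This makes 4 × 2 = 8 strata of about 64/8 = 8 subjects.

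The test is taken as CMH general association. In stratum h there are n_h subjects and t_h responders; a_h holds the responder counts in cohorts 1–3, and p_h those cohorts' shares of the stratum:

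Q = S′V⁻¹S, with S = Σ(a_h − t_h p_h) and V = Σ [t_h(n_h − t_h)/(n_h − 1)] [diag(p_h) − p_h p_h′],

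compared with the chi-square distribution on 3 df (critical value 7.81). Each scenario used at least 2,000 simulated trials, so a proportion near 0.32 has a Monte Carlo standard error of about √(0.32 × 0.68/2000) = 0.01. Severity is balanced and has no effect on response:

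| Assumed rates, cohorts 1–4 | Regression runs | True difference, cohort 4 − 1 | Mean estimate when it runs |
|---|---|---|---|
| 0.60 in all | 5% | 0 | −0.02 |
| 0.45/0.55/0.65/0.75 | 28% | 0.30 | 0.46 |
| 0.50/0.61/0.72/0.80 | 32% | 0.30 | 0.45 |
| 0.40/0.55/0.70/0.85 | 64% | 0.45 | 0.53 |
| 0.30/0.50/0.70/0.90 | 92% | 0.60 | 0.62 |

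Both the chance of no regression and the inflation shrink as the true dose effect grows.

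**4. Effect of omitting severity**

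Further assumptions: severity shifts the log-odds of response by ±1, and dose rates before that shift are 0.45/0.55/0.65/0.75. The true difference is then 0.247. Estimates here are averaged over all trials, before any conditioning on the CMH test.

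| Severe share by cohort | Dose + site | Dose + site + severity |
|---|---|---|
| 50% in each | 0.251 | 0.251 |
| 35/45/55/65% | 0.124 | 0.252 |

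With no dose effect (0.60 in all) and the same imbalance, the model without severity gives −0.133 and the adjusted model −0.001. At 0.40/0.55/0.70/0.85 with that imbalance the loss is smaller: 0.282 without severity, against a true 0.387.

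**5. Sparse data**

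A cohort with a true rate of 0.9 has probability 0.9¹⁶ = 0.185 of 16 responders out of 16. Ordinary maximum-likelihood logistic regression then has no finite estimate for that dose.

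**The case against.** A reader might infer that the dose-response estimate for the primary endpoint is wrong or absent. The documents do not support that. Cohort rates with exact intervals, the severity- and center-stratified CMH test and the exact trend test are all unconditional. So is the adjusted model for change from baseline, which compares doses on the same scale. A logistic model remains permitted. This part of the objection stands, and it limits the point to one missing item.

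Nor is a linear model on a binary outcome an error in itself. With categorical dose it estimates risk differences, and with balanced severity and no conditioning it is unbiased (0.298 against a true 0.300 at 0.45–0.75). Fitted values outside 0–1 do occur in simulation, but such counts include trials where the CMH condition would stop the model being fitted, and nothing legible plans to report fitted probabilities.

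Protocol 9.4 calls group comparisons exploratory and leaves detailed methods to the SAP. The sample size is not power-based, and escalation rests with the Data Review Committee. No confirmatory claim is at risk. But the SAP may refine the protocol's model only if it does so coherently, and 6.5.1 and 6.5.4 disagree with each other.

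Parts of SAP 6.5 are redacted and the table shells are a separate document. An adjusted model could be specified there, so the finding covers the legible text only.

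**Conclusion.** The conflict is plain in the text and should be corrected. For the binary primary endpoint, SAP 6.5.1 mandates only a linear, conditional regression without severity, and the unconditional severity-adjusted dose comparison called for by Protocol 9.4.1 and SAP 6.5.4 is not specified.

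The size depends on assumed rates. The regression would run in about 32% of trials at 0.50/0.61/0.72/0.80 and about 64% at 0.40/0.55/0.70/0.85. In the first case the reported cohort difference would average about 0.45 against a true 0.30.

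Bias from omitting severity arises only if severity both affects response and differs between cohorts. Investigators are asked to aim for an even split, but nothing enforces it. With 35–65% severe across cohorts and a log-odds effect of ±1, the difference is roughly halved at rates of 0.45–0.75; with even severity there is no bias. Because the analysis is exploratory and several unconditional outputs exist, this is a correction to make, not a flaw that undermines the trial.

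**What to change.** In SAP 6.5.1, replace the conditional linear regression with:

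*Regardless of the CMH result, Week 4 response will be analysed by logistic regression with dose (categorical), baseline IGA-LCWS severity and study center, using a sparse-data method (Firth or exact), with estimates and 95% CIs by dose.*

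Choose Firth or exact before the analysis is run, and make SAP 6.5.4 refer to this model by name. The unstratified logistic model may stay if it is labelled a sensitivity analysis.

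This brings the SAP into line with Protocol 9.4.1, so no protocol change is needed. The cost is SAP wording and one extra program, with no new data. Intervals will be wide with about 16 subjects per cohort, and the result stays exploratory.

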6.5.3.2 Time to Return to, or Time to Loss of, a Given State

The time to return to a given state, or time to loss of a given criterion, will be summarized with point estimates of median duration and 2-sided, 95% CIs, using the log-log transformation by summary cohort. Estimates of survival rates and the 2-sided, 95% CI, using the log-log transformation will also be provided. Kaplan-Meier survival curves will be plotted such that each summary group is a separate line in the same plot. This approach corresponds to the following exploratory endpoints:

- Median time to return to baseline or worse in LCL severity on both the IGA-LCWS and PLCWS at maximum smile

6.5.3.3 Proportions in a Given Category

Changes from baseline in LCL severity will be categorically summarized using number and percentages by summary cohort by visit. Separate summaries will be performed for the IGA-LCWS and the PLCWS.

Subject diary of PLCWS to assess the onset of response (decrease from baseline of at least 1 point) will be summarized categorically.

Responses to the Subject Global Satisfaction with Treatment and FASE questionnaire (subject's perception of how old they think they look following the treatment) at all timepoints after LCL treatment, will be categorically summarized by proportion of subjects with a given response.

6.5.3.4 Descriptive Statistics and Change from Baseline

Responses to the FASE questionnaire at all timepoints after LCL treatment, actual age, number of years older, younger will be descriptively summarized.

Transformed scores for the FACE-Q™ Appraisal of Lines: Crow's Feet will be summarized using descriptive statistics for continuous variables.

Statistical Analysis Plan for 1820205

6.5.4 Adjustments for Covariates

The analysis of the primary endpoint requires a regression model to be run, where the baseline IGA-LCWS severity and study site are included in the model as covariates.

[REDACTED]

[REDACTED]

[REDACTED]

[REDACTED]

[REDACTED]

6.6 Safety Analyses

Safety summaries and analyses will be performed on the Safety population and will be presented by cohort and in total across cohorts. Descriptive statistics will be presented to summarize the safety data. By visit safety summaries will use denominators based on the number of subjects with valid observations at that visit unless otherwise specified.

6.6.1 Extent of Exposure

All subjects are planned to receive LCL treatment. The dosage of investigational product injected and the dose of investigational product injected at each of the injection sites will be summarized overall and by summary cohort for each administration using descriptive statistics (number of non-missing observations, mean, median, first and third quartiles, minimum, maximum, and standard deviation).

6.6.2 Injection Site Evaluations

The injection site evaluations for LCL will be summarized using number and percentage of subjects with a reaction at any post-treatment visit. In addition, the number and percentage of subjects experiencing an AE of special interest related to LCL injection site reactions will be summarized by summary cohort, system organ class, and preferred term.

Statistical Analysis Plan for 1820205

6.6.3 Adverse Events

All AEs will be recorded and classified on the basis of MedDRA terminology. All treatment-emergent AEs will be summarized by summary cohort and overall, system organ class, preferred term, severity, and seriousness. When summarizing events by causality and severity by subject, each subject will be counted only once within a system organ class or a preferred term by using the event with the greatest relationship and highest severity within each classification. In the case of missing AE severity or relationship, the most severe/highest relationship will be imputed. Additionally, some summaries will present the number of AEs as well as incidence.

An overall summary of treatment-emergent AEs (TEAEs) will be provided. The number and percentage of subjects experiencing an AE, an SAE, a related AE, a related SAE, an AE of special interest, an AE leading to study discontinuation, and an AE resulting in death will be summarized.

All information pertaining to AEs noted during the trial will be listed by subject, detailing the verbatim description given by the Investigator, preferred term, system organ class, start date, stop date, severity, action taken regarding trial drug, corrective treatment, outcome, and drug relatedness. The event onset relative (in number of days) to the date of treatment for LCL, as well as to the date of last treatment administration prior to the event, will be provided. In addition, a list of adverse events that lead to the subject's premature discontinuation of the trial will be provided. Serious adverse events (SAEs) will be listed by subject.

6.6.4 Laboratory Tests**6.6.4.1 Clinical Safety Laboratory Parameters**

Laboratory test results will be summarized with descriptive statistics by visit. Change from baseline to post-baseline visits will be summarized for continuous test results. A summary of abnormal urinalysis incidence will be presented displaying normal, abnormal (not clinically significant), and abnormal (clinically significant) results.

Shift tables will be presented to summarize laboratory test results at Baseline and Final Evaluation Visit. Normal ranges established by the central laboratory will be used to determine shifts. A listing of all out-of-range laboratory test results at any evaluation will also be provided. Determination of clinical significance for all out-of-range laboratory values will be made by the investigator and included in the listing. In addition, a listing of all clinically significant laboratory test results will be provided.

6.6.4.2 Pregnancy Tests

Urine pregnancy tests will be presented in data listings for all treated subjects in the category of woman of child-bearing potential.

Statistical Analysis Plan for 1820205

[REDACTED]

[REDACTED]

[figure not shown]
6.6.6 Vital Signs and Physical Examination

[figure not shown]
Vital signs and ECG parameters will be summarized by cohort with descriptive statistics by visit. Vital signs and ECG parameters will summarize the actual value as well as the change from baseline for each visit for continuous parameters.

[figure not shown]
Abnormal findings from the physical examination will be summarized by body system and cohort using number and percentage of subjects with a normal, abnormal and clinically significant, or abnormal and not clinically significant result.

[figure not shown]
[REDACTED]

[figure not shown]
Statistical Analysis Plan for 1820205

[figure not shown]

[figure not shown]

[figure not shown]

[figure not shown]

Statistical Analysis Plan for 1820205

[figure not shown]

Statistical Analysis Plan for 1820205

Statistical Analysis Plan for 1820205

Statistical Analysis Plan for 1820205
